9.4.1.1 Multiplicity adjustments

A hierarchical testing procedure will be used for adjustment of multiplicity for the testing of NI and superiority on the primary endpoint and in the analysis of the secondary endpoints to strongly control the overall Type-1 error rate at 0.05, with the hierarchy defined as:

- Non-inferiority (1.8 and 1.3 margin) of efpeglenatide versus placebo on 3-point MACE (CV death, non-fatal MI or non-fatal stroke), and then Superiority of efpeglenatide versus placebo on 3-point MACE (CV death, non-fatal MI or non-fatal stroke)
- Superiority of efpeglenatide versus placebo on time to the first occurrence of the expanded cardiovascular outcome of cardiovascular death, non-fatal MI, non-fatal stroke, coronary revascularization, or unstable angina
- Superiority of efpeglenatide versus placebo on time to the first occurrence of any of the following clinical events: new onset or progression to macro albuminuria (>300 mg/g) accompanied by a UACR value increase of $\geq 30\%$ from Baseline, sustained $\geq 40\%$ decrease in eGFR from Baseline (for ≥ 30 days), chronic dialysis (for ≥ 90 days), renal transplant, sustained eGFR < 15 mL/min/1.73 m² (for ≥ 30 days)

9.4.2 Safety analyses

All safety analyses will be performed on the Safety Population.

The **observation period of safety data** is divided into 3 main segments:

- The pre-treatment period is defined as the time from informed consent up to the time of the first injection of IMP
- The on-treatment period is defined as the time from the first injection of IMP up to 30 days after the last injection of IMP
- The post-treatment period is defined as the time starting 31 days after the last injection of IMP (after the on-treatment period)

The AE observations will be classified per the observation periods of safety data as defined above into:

- **Pre-treatment AEs** are AEs that developed or worsened or became serious during the pre-treatment period
- **Treatment-emergent AEs** are AEs that developed or worsened or became serious during the on-treatment period
- **Post-treatment AEs** are AEs that developed or worsened or became serious during the post-treatment period.

The primary focus of AE reporting will be on TEAEs. Pre-treatment and post-treatment AEs will be described separately.

In addition to the on-treatment period, all AEs, SAEs, AEs leading to permanent treatment discontinuation, and AEs leading to death will be summarized for the on-study period, which is defined as the time from randomization up to the day of recorded end of study or last contact.

Table 8 - Safety analyses

Endpoint	Statistical Analysis Methods
AE	All AEs will be coded to a lowest level term (LLT), preferred term (PT), high level term (HLT), and high level group term (HLGT) and associated SOC using the version of MedDRA currently in use by the Sponsor at the time of DB lock.
SAE	
AE leading to treatment discontinuation	Adverse event incidence tables will be presented by primary SOC (sorted by internationally agreed order), HLGT, HLT and PT (sorted in alphabetical order) for each treatment group, showing the number (n) and percentage (%) of participants experiencing an AE.
AE leading to death	Adverse event incidence table will be provided by treatment group for all types of TEAEs: all TEAEs, all treatment emergent SAEs, all TEAEs leading to permanent treatment discontinuation, all TEAEs leading to death, all AESI, and AE requiring specific monitoring.
AESI	
AE requiring specific monitoring	
Vital signs and laboratory data	Adverse event incidence table for all types of TEAE will also be provided by treatment group in the subsets of participants on the background therapy of metformin + SGLT2, and on metformin + sulfonylurea.
ECG	For quantitative safety parameters based on central laboratory/reading measurements, descriptive statistics will be used to summarize results and change from Baseline values by visit and treatment group.
	The incidence of potentially clinically significant abnormalities (PCSA), defined as abnormal values

Endpoint	Statistical Analysis Methods
	considered medically important by the Sponsor according to predefined criteria/thresholds based on literature review, will be summarized at any time during the on-treatment period. Results will be presented both in standard international and conventional US units The incidence of Normal and Abnormal ECG status at any time during the on-treatment period will be summarized by treatment group whatever the Baseline level and according to Baseline status.
Exploratory	Will be described in the statistical analysis plan finalized before DB lock

HLGT: higher-level grouped term; HLT higher-level term; LLT: lower-level term; PT preferred term; SOC: system organ class; TEAE treatment-emergent adverse event

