- Gastrointestinal AEs, in particular, nausea, were the most common. The trend over time for nausea and vomiting events appeared dose related with an increase after the first injection, and generally decreasing thereafter. In studies where a titration phase (ie, where a schedule of gradual dose escalation up to the randomized dose) occurred, the effect was less pronounced during the titration phase. The percent of TEAEs, discontinuations and nausea and vomiting appeared to be dose dependent.
- There were no reports of pancreatitis.

- TEAEs leading to discontinuation in the GI disorders system organ class (SOC) for efpeglenatide in Studies HM-EXC-203, HM-EXC-204 and HM-EXC-205 (the large Phase 2 studies) were 2.2%, 8.3% and 9.8%, respectively.
- There was one case of medullary thyroid cancer and one case of pancreatic cancer reported in the Phase 1 and 2 programs. They were considered by the investigators to be unrelated or unlikely related to efpeglenatide respectively.
- No serious or severe immunogenicity events (eg, allergic reactions or immune complex disease and injection site reactions) were reported.
- No severe hypoglycemia was reported.
- No fetal toxicity was reported.
- Elevated ALT levels ≥ 3 x upper limit of normal (ULN) post-baseline were seen in 15 of 754 subjects in the large Phase 2 studies (HM-EXC-203 and HM-EXC-204 in patients with T2DM and HM-EXC-205 in obese subjects); 2 of 147 subjects on placebo, 12 of 571 subjects on efpeglenatide, and 1 of 36 subjects on liraglutide. There were several confounding factors such as acetaminophen (paracetamol) used and elevated levels at either baseline or screening. None of these subject experienced increased bilirubin >2 x ULN. Four of the 15 subjects discontinued study medication due to abnormal liver function tests. There were no cases of ALT increase ≥ 3 x ULN in the Phase 1 studies (HM-EXC-101 and HM-EXC-102) and the Phase 2 studies (HM-EXC-201 and HM-EXC-202).
- Diabetic retinopathy complications have been reported for one of GLP-1 RAs (as of 05 December 2017). No case has been reported for efpeglenatide.
- The 24-hour ECG performed in Study HM-EXC-102 showed that the increase of heart rate (HR) seen with 6 mg efpeglenatide was in the range of liraglutide 1.8 mg.
- There were no deaths in the studies.

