4.4 END OF STUDY DEFINITION

A participant is considered to have completed the study if he/she has completed the Study Closeout Visit (in person or by phone) or has died prior to the Study Closeout Visit.

The study is event driven and will continue until it is projected that 330 participants will have at least one primary event (3-point MACE) positively adjudicated by the CEC.

All randomized patients will be asked to return to the study site for a Study Closeout Visit when approximately 330 participants have at least one primary event (3-point MACE) positively adjudicated by the CEC. The timing and window of this visit will be communicated to sites once the date on which the required number of events is projected to be positively adjudicated has been determined.

For patients who previously prematurely permanently discontinued IMP, the Study Closeout Visit, planned at least 6 weeks after the pEOT visit for post-treatment follow-up, will be the final study visit. Participants still taking the IMP at the time of the Study Closeout Visit will have their final study visit (Follow-up Visit) 6 weeks after their Study Closeout Visit.

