#### ***Observation period***

The observation period will be divided into 3 periods:

- The pre-treatment period or screening period is defined as the time from signed informed consent up to the time of first injection of the double-blind IMP
- The treatment-emergent adverse event period (on-treatment period) is defined as the time from the first injection of the IMP to the last injection of the IMP + 30 days (or +7 days for hypoglycemia).
- The posttreatment period is defined as the period after the end of the treatment-emergent adverse event period.

The on-study observation period/on-study is defined as the time from first IMP until the end of (the) study date (defined as the last scheduled visit for those who completed the study and the study discontinuation date collected on eCRF form 'Completion of End of Study' for those who did not complete the study. If death is reason collected on the 'Completion of End of Study' form, date of death will be used).

The post-study observation is defined as anything after the on-study observation period.

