## 2.2.4 Safety population

The Safety Population is defined as:

- All randomized participants who have received at least 1 dose of double-blind treatment, regardless of the amount of treatment administered. Participants will be analyzed according to the treatment actually received.

In addition:

- Nonrandomized but treated patients will not be part of the safety population; however, their safety data will be presented separately.
- For participants receiving 1 or more injections of efpeglenatide during the trial, regardless of being assigned to the efpeglenatide groups or not, the treatment group allocation for as-treated analysis will be included in the efpeglenatide dose group that they are exposed for longer duration (by counting the number of kits received). In case of tie, highest dose group will be used.
- Participants, who prematurely and permanently discontinued study treatment during the titration phase will be summarized in their planned treatment group for as-treated analysis.
- Randomized patients for whom it is unclear whether they took the IMP will be included in the safety population in their planned treatment group.
- Randomized patients will be excluded from the safety population only if there is documented evidence (i.e., all study dates recorded as no medication taken) that patients have not taken the study treatment. If a patient is dispensed double-blind IMP and is lost to follow-up without any documented evidence, the patient will be considered exposed.

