#### ***2.3.5.1 Analyses of adverse events***

##### ***Generalities***

The primary focus of AE reporting will be on TEAEs. Pretreatment and posttreatment adverse events will be described separately.

If an adverse event date/time of onset (occurrence, worsening, or becoming serious) is incomplete, an imputation algorithm will be used to classify the adverse event as pretreatment, treatment-emergent, or posttreatment. The algorithm for imputing date/time of onset will be conservative and will classify an adverse event as treatment emergent unless there is definitive information to

determine it is pretreatment or posttreatment. Details on classification of adverse events with missing or partial onset dates are provided in [Section 2.5.3](#).

Adverse event incidence tables will present by SOC and PT, sorted in alphabetical order for each treatment group, the number (n) and percentage (%) of patients experiencing an adverse event. Multiple occurrences of the same event in the same patient will be counted only once in the tables within a treatment phase. The denominator for computation of percentages is the safety population within each treatment group.

Sorting within tables ensures the same presentation for the set of all adverse events within the observation period (pretreatment, treatment-emergent, and posttreatment). For that purpose, the table of all TEAEs presented by SOC and PT sorted by the internationally agreed SOC order and decreasing frequency of PTs within SOCs will define the presentation order for all other tables unless otherwise specified. Sorting will be based on incidence in the pooled efpeglenatide group.

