### ***Analysis of pretreatment and posttreatment adverse events***

- All pretreatment AEs by primary SOC and PT, showing the number (%) of patients with at least 1 pretreatment adverse event
- All posttreatment AEs by primary SOC and PT, showing the number (%) of patients with at least 1 posttreatment adverse event
- All posttreatment SAEs by primary SOC and PT, showing the number (%) of patients with at least 1 posttreatment serious adverse event

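### Post-treatment AE and SAE percentages are taken over the whole safety population, so they mainly reflect how many participants stopped early and when

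*Protocol*

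**What the plan says.** Protocol 9.4.2 defines the period: "The post-treatment period is defined as the time starting 31 days after the last injection of IMP (after the on-treatment period". SAP 2.1.4 (Observation period) agrees: "The posttreatment period is defined as the period after the end of the treatment-emergent adverse event period". Neither definition states when the period ends.

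The denominator rule is in SAP 2.3.5.1, under Generalities: "The denominator for computation of percentages is the safety population within each treatment group". SAP 2.2.4 defines that population as: "All randomized participants who have received at least 1 dose of double-blind treatment, regardless of the amount of treatment administered". Whether someone has any post-treatment follow-up plays no part in it.

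Later in SAP 2.3.5.1, two tables are planned for the post-treatment period: "All posttreatment AEs by primary SOC and PT, showing the number (%) of patients with at least 1 posttreatment adverse event" and "All posttreatment SAEs by primary SOC and PT, showing the number (%) of patients with at least 1 posttreatment serious adverse event". No other denominator and no rate is given for them.

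Follow-up after the last injection depends on when IMP ends. Under protocol 4.4, participants still taking IMP at close-out "will have their final study visit (Follow-up Visit) 6 weeks after their Study Closeout Visit". Under protocol 4.1, participants who stop IMP early stay in follow-up until close-out or death. Protocol 8.3.1 collects AEs and SAEs up to the follow-up visit. Planned follow-up is 24 to 36 months (protocol 9.2, SAP 1.3).

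**The concern.** A percentage of participants with an event is comparable between arms only if the time at risk is comparable. Here it is not. Nearly all post-treatment person-time belongs to early stoppers, but the denominator counts everyone who was treated. The figure printed for each arm is therefore roughly the share who stopped early multiplied by their risk over whatever time was left, plus a small contribution from everyone else.

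If stopping differs between arms in frequency or in timing, the tables differ even when the drug has no effect after it is stopped. A reader of a by-arm post-treatment SAE table could take that for a delayed or withdrawal effect, or could overlook a real one if the imbalance runs the other way. Unequal stopping is plausible: on the Phase 1 and 2 studies, protocol 2.3 says "The percent of TEAEs, discontinuations and nausea and vomiting appeared to be dose dependent".

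**Working it through.** The plan states no post-treatment incidence, so there is no figure of its own to reproduce. The check asks what the planned tables would show if the true post-treatment hazard were the same in every arm.

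**Inputs from the documents**
- The post-treatment period starts on day 31 after the last injection (protocol 9.4.2, SAP 2.1.4).
- Participants on IMP to close-out: 6 weeks = 42 days, and 42 − 30 = 12 days = 12/365.25 = 0.0329 years.
- Early stoppers: followed to close-out, within a planned 24 to 36 months.

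**Assumptions (not in the documents)**
- Share stopping early, *s*: 10%, 15% or 20%.
- SAE hazard *r*: 0.15 per patient-year, the same in all arms and in stoppers and completers; varied from 0.10 to 0.30.
- Post-treatment time of early stoppers: 1.5 years on average, treated as fixed.

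**Planned percentage**

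p = s·(1 − e^(−1.5r)) + (1 − s)·(1 − e^(−0.0329r))

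At r = 0.15 the two risks are 1 − e^(−0.225) = 0.2015 and 1 − e^(−0.00493) = 0.0049.

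| Stopping share | From stoppers | From the rest | Planned % | Ratio to 10% |
|---|---|---|---|---|
| 10% | 0.0201 | 0.0044 | 2.46 | 1 |
| 15% | 0.0302 | 0.0042 | 3.44 | 1.40 |
| 20% | 0.0403 | 0.0039 | 4.42 | 1.80 |

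The true ratio is 1. At r = 0.10 the ratios are 1.40 and 1.81; at r = 0.30 they are 1.39 and 1.78. If the last weekly injection falls 7 days before close-out, completers have 19 days instead of 12, and at r = 0.15 the ratios are 1.36 and 1.71.

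Share of post-treatment person-time held by stoppers: at s = 10%, 0.15/(0.15 + 0.90 × 0.0329) = 84%; at s = 20%, 0.30/(0.30 + 0.80 × 0.0329) = 92%.

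**Varying the stop times.** A simulation of 2 million participants per arm used follow-up uniform over 2 to 3 years and hazards of 0.10 and 0.20. Stopping was either uniform over follow-up (mean 1.17 post-treatment years for stoppers) or mostly early (mean 1.92 years). The false ratio was 1.36 to 1.42 for 15% against 10%, 1.74 to 1.83 for 20% against 10%, and 2.11 to 2.25 for 25% against 10%.

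**Timing alone.** With 10% stopping in both arms and hazard 0.10, the planned percentage is 1.37% under uniform stopping and 2.03% under mostly early stopping. The ratio is 2.03/1.37 = 1.48 with equal shares.

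**Which presentations remove the artefact**
- *First events per patient-year.* Over a post-treatment time T, the expected time to first event or end is (1 − e^(−rT))/r. Expected events divided by expected time at risk therefore equals r whatever the mix of T, which is 15 per 100 patient-years in every arm at r = 0.15. The simulation gave about 10.0 and 20.0 per 100 patient-years at hazards 0.10 and 0.20, at every stopping share.
- *Percentage among early stoppers only.* At hazard 0.10 with uniform stopping this is 10.7% to 10.8% at every stopping share. With mostly early stopping it is about 17.3%, so the split removes the effect of share but not of timing. It needs the rate beside it.
- *On-study table.* The ratios are 0.99 to 1.00.

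**The case against.** The strongest reply is that little depends on these tables. Treatment-emergent events are the stated focus, no safety testing is planned (SAP 2.3.5), and the on-study AE and SAE tables compare the arms over nearly equal follow-up. The absolute gap in the example is 3.44 − 2.46 = 0.98 or 4.42 − 2.46 = 1.96 percentage points for any SAE, spread over many SOC and PT rows. All of this stands, and it sets the severity. It does not make the two tables correct: the on-study tables merge time on and off drug, so they cannot show whether an apparent post-treatment excess is real.

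Three stronger readings are tempting, and the documents do not support them.

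- *The tables will show a dose-ordered excess on efpeglenatide.* This needs more stopping on active drug in this trial, and neither document gives stopping rates by arm. The dose-dependence statement describes Phase 1 and 2 experience. The Phase 2 gastrointestinal discontinuation figures beside it (2.2%, 8.3% and 9.8%) have no placebo comparator. The same section reports that nausea and vomiting were less pronounced under titration, which both active arms use here. If placebo participants stop more, the false excess falls on placebo.
- *Every AE percentage in the SAP is affected.* The safety-population denominator is a general default. Nausea, vomiting and diarrhea over time use participants at risk at the start of each interval, severe hypoglycemia has events per 100 patient-years, and PCSA percentages use patients assessed in the period.
- *A real post-treatment signal could not be recognized.* SAP 2.2 plans discontinuation counts by reason and Kaplan-Meier plots of permanent discontinuation. The SAE listings carry onset and treatment-discontinuation dates. A careful reader could work back from these, though the tables themselves would not help.

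**Conclusion.** The concern holds for the two post-treatment tables in SAP 2.3.5.1 and for nothing wider. Under the stated denominator their percentages are driven mainly by the share and timing of early stopping. With equal true hazards, the false ratio is about 1.4 for 15% against 10% stopping and about 1.8 for 20% against 10%.

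That early stoppers and completers have very different post-treatment follow-up comes from the documents. The size of any false difference rests on assumed stopping shares, stop times and SAE rates, and its direction on which arm stops more or earlier; if stopping is alike in all arms there is none. No primary, secondary efficacy or treatment-emergent result is touched. Severity is minor.

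**What to change.** In SAP 2.3.5.1, for the post-treatment AE and SAE tables:

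1. Report, by arm, participants with a first post-treatment event per 100 patient-years of post-treatment follow-up. Count time from day 31 after the last injection to the first such event or the end of study date, and state that end point, since the period has none at present.
2. Show early IMP stoppers separately from participants who have only the close-out-to-follow-up interval.
3. Add a footnote that comparisons among stoppers are not protected by randomization, because stopping happens after it and may depend on treatment, and that the on-study tables carry the between-arm comparison.

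Restricting the denominator to participants observed beyond last injection + 30 days would not work. Completers also pass day 30 and stay in it, so 2.46% against 3.44% remains a ratio of 1.40.

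The cost is SAP wording and somewhat more work on two tables. The dates are already needed to define the safety periods. The rate is most easily read when the hazard is roughly constant, which is a modest assumption for a descriptive table. The change should be made before database lock.

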9.4.3 Other analyses

Exploratory analyses will be described in the statistical analysis plan finalized before DB lock.

9.5 INTERIM ANALYSES

There is no interim analysis planned.

9.5.1 Data Monitoring Committee (DMC)

See Appendix 1 ([Section 10.1.4](#)) for details.

10 SUPPORTING DOCUMENTATION AND OPERATIONAL CONSIDERATIONS

10.1 APPENDIX 1: REGULATORY, ETHICAL, AND STUDY OVERSIGHT CONSIDERATIONS

10.1.1 Regulatory and Ethical Considerations

- This study will be conducted in accordance with the protocol and with the following:
 - Consensus ethical principles derived from international guidelines including the Declaration of Helsinki and Council for International Organizations of Medical Sciences (CIOMS) International Ethical Guidelines
 - Applicable International Conference on Harmonisation (ICH) Good Clinical Practice (GCP) Guidelines
 - Applicable laws and regulations
- The protocol, protocol amendments, ICF, IB, and other relevant documents (eg, advertisements) must be submitted to an IRB/IEC by the Investigator and reviewed and approved by the IRB/IEC before the study is initiated.
- Any amendments to the protocol will require IRB/IEC approval before implementation of changes made to the study design, except for changes necessary to eliminate an immediate hazard to study participants.
- The Investigator will be responsible for the following:
 - Providing written summaries of the status of the study to the IRB/IEC annually or more frequently in accordance with the requirements, policies, and procedures established by the IRB/IEC
 - Notifying the IRB/IEC of SAEs or other significant safety findings as required by IRB/IEC procedures
 - Providing oversight of the conduct of the study at the site and adherence to requirements of 21 Code of Federal Regulations (CFR), ICH guidelines, the IRB/IEC, European regulation 536/2014 for clinical studies (if applicable), and all other applicable local regulations

